The qualifications of all the staff are included in the protocol itself and in the attached summary. The staff conducting research in Malawi is [name], BCM. In addition, the other people assisting will be the other faculty listed on the protocol. All other physicians, connections, and support staff within each country are described in the protocol and summary; many are Baylor College of Medicine faculty, and largely will not be conducting research as much as they will be assisting with country logistics.

Although there is therapeutic intent, all subjects enrolled are in Malawi and thus Medicaid/Medicare does not apply.

A7. Research Category:**A8. Therapeutic Intent**

Does this trial have therapeutic intent?

No

A9. ClinicalTrials.gov Registration

Does this protocol/trial require registration on ClinicalTrials.gov due to it: meeting the definition of an Applicable Clinical Trial, being required under the terms and conditions of an award, or being proposed to be published in ICMJE journals?

No, this clinical is not a clinical trial, or does not meet the definition of an Applicable Clinical Trial, or does not need to be registered under the terms and conditions of an award, or is not a clinical trial with results intended to be reported in an journal belonging to the ICMJE. Registration is not required.

Section B: Exempt Request**B. Exempt From IRB Review**

Not Applicable

Section C: Background Information

The burden of perinatal morbidity and mortality related to preterm birth is astounding. In 2005, the WHO estimated that 9.6% or 12.9 million births worldwide were born preterm at <37 weeks of gestation, and were accompanied by as high as a 42% mortality rate (<http://www.who.int/bulletin/volumes/88/1/08-062554>). Despite regional advances and slight decreases in the U.S. preterm birth rate in the last two years, adverse birth outcomes related to the length of gestation (preterm birth and near-term birth) are recognized as one of the most significant disorders in maternal-child health at global scale. Worldwide, more than 20 million infants are born each year with low birth weight, with more than 95% of these being delivered in developing nations (1, 2). Of the 4 million newborn deaths annually, nearly 1/3 (27%) are directly attributable to prematurity with another 36% secondary to opportunistic infections (sepsis, pneumonia, gastrointestinal) related to prematurity and low birth weight (1). 75% of the 4 million deaths occur within the first week of life, with the vast majority occurring in the first 48 hours (1, 2). In poor rural communities, infant mortality related to preterm and low birth rate birth exceeds that in urban communities, and is not solely attributed to limited access to secondary and tertiary care (1). Because the empiric recurrence risk of preterm birth approximates 40-50% (3), global primary prevention of preterm birth is essential (4).

Identifiable causes of preterm birth are generally ascribed to one of three categories: 45-50% idiopathic, 30% in association with preterm premature rupture of the membranes, and 15-20% are iatrogenic or maternally indicated (5). However, multiple factors including modifiable behaviors (smoking), maternal periodontal disease, prior history of preterm birth, multiple gestations, race/ethnicity (African-American women have a higher risk than Caucasians), and foreshortened cervical length (where at <25 weeks 2.0 cm is the 5th%, and 2.5 cm is the 10th%) have been postulated to influence the occurrence of preterm births (6-9). The combination of two or more factors can possibly synergistically or additively increase the risk for spontaneous preterm birth. For example, in addition to identifying polymorphisms rendering susceptibility of risk for the delivery of preterm and growth restricted births (10,11), we have previously demonstrated that maternal tobacco use in pregnancy meaningfully alters the placental epigenome and subsequent gene expression (12,13). Accurate determination of the relative and additive or synergistic

contribution of underlying etiologies, such as periodontal disease and oral health with behavioral and socioeconomic factors are hampered by a fundamental lack of understanding of the process of parturition (5, 12-16). As such, the cause(s) of as great as 80% of spontaneous preterm births remain classified as ‘unknown’ (1-5). However, maternal oral health is emerging as a leading contributor to risk of spontaneous and infectious-related preterm birth on a global scale (7-9; 17-26).

Pertaining to the soundness of the observations, 195 studies in the 16 years since Offenbacher’s original observations (17) have been published (PubMed search, March, 2014) and the overwhelming majority demonstrate a link between poor maternal oral health and risk of preterm birth (example references 17-33).

As noted, a relationship between maternal oral health and risk of preterm birth and low birth weight infants has long-been demonstrated (17, 18; 27-29) in both industrialized nations (17-19) and rural and developing regions (27-30). In initial data from two single-center clinical trials, periodontal treatment in gravidae with dental caries reduced the rate of preterm birth (31,32). However, more definitive analysis from three large, multicenter randomized controlled trials have failed to show a benefit to non-surgical treatment for periodontitis (inflammation secondary to periodontal infection), specifically ‘scaling and root planing’ (i.e., removal of dental plaque and calculus from the tooth enamel and root; 19, 20, 33). In sum, three observations persist: 1. Peridental disease in gravidae poses risk of preterm birth and delivery of a low birth weight infant globally; 2. However, treating periodontal disease by scaling and root planing in gravidae who manifest such oral microbial inflammation poses no benefit to the prevention of preterm birth, but also no harm (i.e., it improved periodontal disease but did not decrease nor increase the risk of preterm delivery); 3. It is unknown whether primary prevention of dental caries and periodontitis may show benefit (identified gap in our knowledge and justification for our proposed study).

Periodontitis (defined as a destructive inflammation of the periodontium) has a prevalence of 30% or greater in women of child bearing age (8, 34). By definition, it involves microbial infiltration of the periodontium, which stimulates a chronic inflammatory response, recurrent bacteremia, and the production of cytokines and prostaglandins which trigger risk of preterm birth (17-34). It is the same production of prostaglandins (primarily PGE2 and reactive intermediates) which are felt to mediate the risk of preterm birth (2-9).

In the last year, we and others have made breakthroughs towards understanding the link between maternal oral health and risk of preterm birth (35-45). A recent cross-sectional study of 195 patients (35) demonstrated Gram-positive and Gram-negative intracellular bacteria harbored in the basal plate (which comprises the tissue layer directly at and below the maternal-fetal interface). These were observed in nearly 1/3 of placental specimens, with a high prevalence among preterm deliveries <28 weeks gestation but regardless of clinical or pathologic evidence of chorioamnionitis (35). Although current paradigms suggest that the majority of intrauterine infections which are associated with preterm birth originate in the lower genital tract and ascend into an otherwise ‘sterile’ intrauterine environment (36), we have most recently demonstrated that the majority of taxa detected in the placenta with DNA-based technology are not found in the urogenital tract, but rather represent commensal species common to the oral cavity (37-42). Some of these oral microbes, such as *Fusobacterium nucleatum* (a Gram-negative oral anaerobe) may facilitate hematogenous transmission during placentation as a result of their ability to bind vascular endothelium and alter permeability, thereby functioning as an ‘enabler’ for other common commensals, such as *Escherichia coli* (37; 42-45). The results of our study (37) indicate that the placenta harbors a low-abundance but metabolically rich microbiome. The placental microbiome is largely comprised of non-pathogenic commensal microbiota from the Firmicutes, Tenericutes, Proteobacteria, Bacteroidetes, and *Fusobacteria* phyla. In aggregate, the placental microbiome profiles were most akin (Bray-Curtis (B-C) dissimilarity <0.3) to the non-pregnant human oral microbiome. 16S-based OTU analyses revealed a strong and significant correlation of the placental microbiome with risk of preterm birth <37 weeks (p=0.001; These latter findings further highlight the likely underlying biologic and molecular mechanisms linking maternal oral health to preterm birth which serves as additional rationale to our clinical trial as proposed herein.

So if we know that there is biologic evidence linking maternal oral health to preterm birth, but treating active periodontal disease does not reduce these morbidities, is it possible that primarily preventing periodontitis (or lessening its severity) might prevent preterm birth? If so, what are the least expensive, practical, and efficacious preventative measures? Globally, many strategies related to prevention of dental caries have focused on reduction of dietary simple sugars. One class of substitutes is the polyols (i.e., sugar alcohols), the most common and efficacious of which include xylitol used in chewing gum such as Spry and ‘sugar free’ gummy snacks. What makes the polyols attractive candidates for the prevention of oral disease (notably in a rural population) is based on these well-grounded observations (references 46-52): 1. In rural communities, where running water, lack of toothpaste and toothbrushes, and inadequate dental care are realities of everyday life, distribution of polyol gum or gummy candies is an attractive alternative; Although research gaps exist on optimal dosing, meta-analyses and multiple prospective and randomized controlled trials demonstrate that xylitol containing chewing gum prevent periodontitis (level I evidence); 2. While the mechanism of action by which the polyols reduce dental caries is uncertain, it is clear that they are efficacious. Hypothesized mechanisms include increasing salivary flow by mastication, enhancing alkaline pH to minimize demineralization/promote remineralization of tooth enamel, and altering the oral microbiome via diminishing abundance of virulent species *Streptococcus mutans*; 3. Xylitol chewing gum has been demonstrated by other investigators to (1) prevent otitis media (double blind, randomized controlled trial, and (2) maternal consumption prevents dental decay in children at 2 and 5 years of age, even when the children did not chew the gum (level I evidence).


Section D: Purpose and Objectives

Our overarching hypothesis is that comprehensive primary preterm birth prevention, inclusive of maternal oral health with xylitol chewing gum (the intervention), will reduce the rate of periodontal disease and caries, preterm birth prevalence, and neonatal mortality. We propose two aims to test our hypothesis: *1* Aim 1 (primary outcome). Our primary aim will be to determine the impact of xylitol gum on the (1) rate of preterm birth <37 and <34 weeks gestation, (2) rate of <2000 gram infants, (3) rate of survival of <2000 gram infants to 30 days, and (4) composite neonatal morbidity of <2000 gram infants at 30 days of age. *2* Aim 2 (secondary outcome). Xylitol chewing gum has been demonstrated by other investigators to prevent otitis media (double blind, randomized controlled trial (RCT), and maternal consumption prevents dental decay in children up to 5 years of age, even when the children did not chew the gum (RCT). In Malawi, where running water and inadequate dental care are realities of everyday life, we will determine whether use of xylitol gum will decrease the prevalence of (1) periodontal disease, and (2) caries among gravidae.

Section E: Protocol Risks/Subjects

E1. Risk Category

Category 1: Research not involving greater than minimum risk.

E2. Subjects

Gender:

Female

Age:

Adult (18-64 yrs)

Ethnicity:

All Ethnicities

Primary Language:

Chichewa

Groups to be recruited will include:

Both patients and healthy, non-patient, normals

Which if any of the following vulnerable populations will be recruited as subjects?

Pregnant women, Women of child bearing potential

Vulnerable populations require special protections. How will you obtain informed consent, protect subject confidentiality, and prevent undue coercion?

Please see Section J.

E3. Pregnant woman/fetus

Will pregnant women and/or fetuses (as described in 45 CFR 46 Subpart B) be enrolled in the research?

Yes

E4. Neonates

Will neonates of uncertain viability or nonviable neonates (as described in 45 CFR 46 Subpart B) be enrolled in the research?

No

E5. Children

Will children be enrolled in the research?

No

Section F: Design/Procedure

F1. Design

Select one category that most adequately describes your research:

z.r) Randomized, Efficacy Study -- Surgical Techniques/Interventions

Discuss the research design including but not limited to such issues as: probability of group assignment, potential for subject to be randomized to placebo group, use of control subjects, etc.

This is a cluster randomized trial. We assessed 12 cluster sites for potential eligibility and excluded 4 sites (around Malawi) because they could not provide reliable delivery data. Of the 8 cluster sites chosen, 4 will be randomly allocated to oral health education and xylitol gum and 4 will be allocated to oral health education and no xylitol gum. The randomization will occur as follows: 1. The first site will be randomized, then computer matched by number of deliveries to the non-intervention site. 2. This process will be repeated in sequence until all 8 sites (4 matched sets) are allocated.

Inclusion Criteria:

The following represent our a priori decided upon inclusion criteria: (1) Enrollment at less than or equal to 20 weeks gestation by best obstetrical estimate; or (2) Enrollment post partum with an anticipated next pregnancy within 18 months; or (3) Enrollment preconception with an anticipated pregnancy within 18 months; and (4) Cognitively aware enough to participate in the study; (5) Greater than or equal to 18 years of age (in Malawi, constitutes a legal adult and capacity to consent for study); (6) Willing to participate in the study; (7) Willing to undergo at least two periodontal exams; (8) Willing to chew 1 piece of xylitol gum for 10 minutes after the morning and evening meal (intervention sites); (9) Anticipating to remain within the region for 18 months.

Exclusion Criteria:

(1) Greater than 20 weeks gestation by best obstetrical estimate; (2) Post partum and not anticipating another pregnancy within 18 months; (3) Preconception and not anticipating another pregnancy within 18 months; (4) Not cognitively aware enough to

participate in the study; (5) Not willing to undergo at least two periodontal exams; (6) Less than 18 years of age; (7) Not willing to chew 1 piece of xylitol gum for 10 minutes after the morning and evening meal (intervention sites); (8) Anticipating a move outside of the region within 18 months.

F2. Procedure

1. Subjects will be recruited by study personnel for potential enrollment during their prenatal visits 2. If enrolled, subjects will be: A) giving medical history/information; B) undergoing a minimum of 2 periodontal exams; (Visit 1 and 2) C) participating in antenatal care; D) chewing xylitol gum (at intervention cluster sites) twice a day following meals; E) undergo delivery (Visit 3) Participants will also be asked to consent to collection of data and potential use of xylitol gum. As previously described, since this product is commercially available over the counter and for the indication of the prevention of dental disease, no IND is necessitated.

Plans for study oversight are as follows: 1. Post-approval, this study will be monitored by the PI and co-PI at BCM in Houston by ensuring that data entry is up to date on a weekly basis. The PI and co-PI will also take regular trips to Malawi to ensure that all study related material is collected and stored according to plan and in compliance with confidentiality requirements. 2. Complaints about the study will be handled by local investigators in Malawi under the guidance of the PI and co-PI at Baylor. 3. Non-compliance on the part of study staff will be addressed by the PI and co-PI. Study staff will be re-educated on study procedures and confidentiality requirements if indicated, and disciplinary action will be taken if appropriate. 4. Unanticipated Problems Involving Risk to Subjects or Others will be handled by local investigators with immediate notification of BCM PIs and co-PIs. Specifically, if there are unanticipated risks or adverse events, then a significant adverse event report will be filed with the Baylor Institutional Review Board and it will also be reported to the Malawi Ministry of Health for evaluation.

Section G: Sample Size/Data Analysis

G1. Sample Size

How many subjects (or specimens, or charts) will be used in this study?

Local: 10360 Worldwide: 10360

Please indicate why you chose the sample size proposed:

Successful engagement in meaningful global research, and notably a randomized trial, necessitates tremendous up-front leg work and demonstration of feasibility. We have invested three years in preparation for the proposed PPax trial and are confident in having now parsed down the necessary components suggesting that we can execute the proposed trial on budget and on time, that we should execute the proposed study testing xylitol gum as an intervention, and that it will take a cluster randomization design enrolling a total sample size of 9360 subjects at 8 proposed sites to demonstrate effect size.

We have estimated that a total sample size of 9360 subjects will be sufficient to demonstrate a 33% reduction in the primary outcomes of (1) preterm birth <37 and <34 weeks, and (2) associated neonatal morbidity and mortality based upon our prior work in Malawi. In our study design (where the health center serves as the unit of randomization), we have accounted for a 30% loss to follow up and calculated our per site enrollment to necessitate 1170 subjects at each of 8 sites.

G2. Data Analysis

Provide a description of your plan for data analysis. State the types of comparisons you plan (e.g. comparison of means, comparison of proportions, regressions, analysis of variance). Which is the PRIMARY comparison/analysis? How will the analyses proposed relate to the primary purposes of your study?

Intercluster (between cluster) analysis will include univariate and multivariate analyses analyzing the number of clusters, average cluster size, range of cluster size, rate of preterm birth, rate of neonatal complications, rate of periodontal disease, rate of maternal comorbidities, range and variance of each measure; analysis by intention to treat and by multivariate measures with GEE. Intracluster (per subject, by cluster) analysis will include univariate and multivariate analyses analyzing the number of subjects, average gestational age, rate of preterm birth, rate of neonatal complications, rate of periodontal disease, rate of maternal comorbidities, range and variance of each measure; analysis by intention to treat and by multivariate measures with GEE.

Section H: Potential Risks/Discomforts

H1. Potential Risks/Discomforts

Describe and assess any potential risks/discomforts; (physical, psychological, social, legal, or other) and assess the likelihood and seriousness of such risks:

The potential risks to participants in this study are minor and include the physical risks associated with some of the sample and data collection, risk of psychological distress, and risks to privacy. a. Physical Risks: Intervention: there are no known significant risks to chewing gum. b. Psychological Risks: There is no recognized potential risk of psychological distress to the study participants as a result of reflecting on their diagnosis and health history. c. Privacy Risks: There is a small, potential risk of loss of confidentiality. Stringent methods described below will be employed to protect against this risk such that this risk is unlikely.

H2. Data and safety monitoring plan

Do the study activities impart greater than minimal risk to subjects?

No

H3. Coordination of information among sites for multi-site research

Is the BCM Principal Investigator acting as the SPONSOR-INVESTIGATOR for this multi-site research?

Yes

Is BCM the COORDINATING CENTER for this multi-site research?

Yes

If the answer to EITHER of the questions above is "Yes", please complete the following questions:

If this is a multicenter study and the BCM PI is an INVESTIGATOR with responsibilities of SPONSOR or if BCM is the COORDINATING CENTER, describe the management of information among the sites related to participant protections. Your description should include reporting of unanticipated problems, protocol modifications, IRB and/or institutional approvals, and interim results among the sites.

We will follow rigorous procedures to ensure the accuracy, quality, and confidentiality of study data. These procedures include staff training and retraining, close supervision, a Manual of Procedures, and quality control reviews.

[name] is a PhD trained bioinformatician with a background in anthropology. He has worked in [name] laboratory since 2008, and designed and implemented the on-line database utilized in the seed grant. He will continue to execute the database and assure quality data with inset custom QA QC measures. He will additionally coordinate the database entry and personnel, and complete the biostatistical analyses on rolling data.

When research is conducted in collaboration with outside entities or organizations, the PI must obtain the necessary approvals from those entities. The BCM IRB may request documentation that such approvals have been obtained. Please list and describe the planned sites for this multi-site research for which the BCM PI is either Sponsor-Investigator and/or Coordinating Center. Sites that do not meet the requirements for inclusion in section A6a of the protocol summary and BCM informed consent documents should be listed here.

Letters of support from Malawi, stating that the Ministry of Health supports the project, are attached. The IRB Approval Letter from the Ministry of Health is also attached.

Section I: Potential Benefits

Describe potential benefit(s) to be gained by the individual subject as a result of participating in the planned work.

Potential benefits may include a reduction in preterm birth and an improvement in oral health.

Describe potential benefit(s) to society of the planned work.

If comprehensive oral healthcare and chewing xylitol gum indeed reduces the risk of preterm birth, society would benefit from this knowledge.

Do anticipated benefits outweigh potential risks? Discuss the risk-to-benefit ratio.

The benefits to the participants and to society outweigh the minimal risks of this project.

Section J: Consent Procedures

J1. Waiver of Consent

Will any portion of this research require a waiver of consent and authorization?

No

J1a. Waiver of requirement for written documentation of Consent

Will this research require a waiver of the requirement for written documentation of informed consent?

No

J2. Consent Procedures

Who will recruit subjects for this study?

PI
PI's staff

Describe how research population will be identified, recruitment procedures, any waiting period between informing the prospective participant and obtaining consent, steps taken to minimize the possibility of coercion or undue influence and consent procedures in detail.

The research population will be drawn from eight clinical sites, all in the greater Lilongwe region of Malawi (a 54 km urban-rural region surrounding Lilongwe). Through BIPAI, TCH and BCM have had a continual presence in this region since 2007 and we have been partnered in this region for obstetrical care since 2011.

Women will be recruited in one of two settings: when they present for prenatal care/ at the time of antenatal booking at less than 20 weeks, or postpartum (on the postpartum ward) or preconception with a desire to have another pregnancy in less than 18 months. Women will be approached by trained and experienced community health workers.

Are foreign language consent forms required for this protocol?

Yes

Which of the following ways will you document informed consent in languages other than English?

A full-length informed consent document

J3. Privacy and Intrusiveness

Will the research involve observation or intrusion in situations where the subjects would normally have an expectation of privacy?

No

J4. Children

Will children be enrolled in the research?

No

J5. Neonates

Will non-viable neonates or neonates of uncertain viability be involved in research?

No

J6. Consent Capacity - Adults who lack capacity

Will Adult subjects who lack the capacity to give informed consent be enrolled in the research?

No

J7. Prisoners

Will Prisoners be enrolled in the research?

No

Section K: Research Related Health Information and Confidentiality

Will research data include identifiable subject information?

Yes

Information from health records such as diagnoses, progress notes, medications, lab or radiology findings, etc.

Yes

Specific information concerning alcohol abuse:

No

Specific information concerning drug abuse:

No

Specific information concerning sickle cell anemia:

No

Specific information concerning HIV:

Yes

Specific information concerning psychiatry notes:

No

Demographic information (name, D.O.B., age, gender, race, etc.):

Yes

Full Social Security #:

No

Partial Social Security # (Last four digits):

No

Billing or financial records:

No

Photographs, videotapes, and/or audiotapes of you:

No

Identifiable biospecimens

No

Other:

No

At what institution will the physical research data be kept?

The physical data is maintained at one of two locations. It is either held securely at the BIPAI Baylor Center of Excellence in Lilongwe, Malawi or in the laboratory of [name] at Baylor College of Medicine, Houston Texas (at study completion).

How will such physical research data be secured?

As described in our protocol, data will be under secure storage and locked in the secured records room at the BIPAI Baylor COE or in the laboratory of [name]. The enrollment logs are kept separate from the data to reduce risk of identifying information being with deidentified (subject codes).

At what institution will the electronic research data be kept?

Baylor College of Medicine. Data is uploaded in a completely deidentified manner on a secure server and maintained at Baylor College of Medicine.

Such electronic research data will be secured via BCM IT Services- provided secured network storage of electronic research data (Non-Portable devices only):

Yes

Such electronic research data will be secured via Other:

No

Will there be anyone besides the PI, the study staff, the IRB and the sponsor, who will have access to identifiable research data?

No

Please describe the methods of transmission of any research data (including PHI, sensitive, and non-sensitive data) to sponsors and/or collaborators.

If sent to collaborators, it is only sent with SSL encryption.

Will you obtain a Certificate of Confidentiality for this study?

No

Please further discuss any potential confidentiality issues related to this study.

There are no further potential confidentiality issues.

Section L: Cost/Payment

Delineate clinical procedures from research procedures. Will subject's insurance (or subject) be responsible for research related costs? If so state for which items subject's insurance (or subject) will be responsible (surgery, device, drugs, etc). If appropriate, discuss the availability of financial counseling.

Subjects will not be charged to participate. There are no ensuant costs to the research. Costs of the xylitol gum are covered by the Thrasher Research Fund and will not be incurred to the subjects.

If subjects will be paid (money, gift certificates, coupons, etc.) to participate in this research project, please note the total dollar amount (or dollar value amount) and distribution plan (one payment, pro-rated payment, paid upon completion, etc) of the payment.

Dollar Amount:

0

Distribution Plan:

Subjects will not be paid to participate in this research project.

Section M: Genetics

How would you classify your genetic study?

Discuss the potential for psychological, social, and/or physical harm subsequent to participation in this research. Please discuss, considering the following areas: risks to privacy, confidentiality, insurability, employability, immigration status, paternity status, educational opportunities, or social stigma.

Will subjects be offered any type of genetic education or counseling, and if so, who will provide the education or counseling and under what conditions will it be provided? If there is the possibility that a family's pedigree will be presented or published, please describe how you will protect family member's confidentiality?

Section N: Sample Collection

None

Section O: Drug Studies

Does the research involve the use of ANY drug* or biologic? (*A drug is defined as any substance that is used to elicit a pharmacologic or physiologic response whether it is for treatment or diagnostic purposes)

No

Does the research involve the use of ANY gene transfer agent for human gene transfer research?

No

O1. Current Drugs

Is this study placebo-controlled?

No

Will the research involve a radioactive drug?

No

Section P: Device Studies

Does this research study involve the use of ANY device?

No

Section Q: Consent Form(s)

PPaX Trial (Prevention of Prematurity and Xylitol) ENGLISH CONSENT

Section R: Advertisements

None

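### Aim 1 measures 30-day survival and morbidity only among infants born under 2000 g, a group formed after allocation, so these outcomes need not track deaths per birth

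*Combined protocol and SAP*

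**What the plan says.** Section D states a hypothesis that includes lower "preterm birth prevalence, and neonatal mortality", with no weight limit. Aim 1, labelled the primary outcome, has four items. Item (2) is "2) rate of <2000 gram infants". Items (3) and (4) are the "rate of survival of <2000 gram infants to 30 days, and (4) composite neonatal morbidity of <2000 gram infants at 30 days of age". The denominator of (3) and (4) is therefore the numerator of (2).

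Section F1 allocates health centres: "4 will be randomly allocated to oral health education and xylitol gum", and the other four receive education alone. Women may also join before they are pregnant: "Enrollment preconception with an anticipated pregnancy within 18 months". The procedures in Section F2 run as far as "undergo delivery (Visit 3").

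Section G1 says the sample size is enough to show "a 33% reduction in the primary outcomes of (1) preterm birth <37 and <34 weeks, and (2) associated neonatal morbidity and mortality". It gives the neonatal part neither a denominator nor a base rate. Section G2 plans intention-to-treat and GEE analyses. It lists neonatal complications without a denominator, does not list mortality, and says nothing about a subset formed after allocation.

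**The concern.** Allocation makes the arms comparable for everything fixed beforehand. It does not do so for a subset picked out by birth weight, which the gum is meant to influence through prematurity. If the gum moves some infants above 2000 g, those left below it in the gum arm differ in number, and probably in mix, from those in the control arm. Intention to treat keeps women in their allocated arm, and GEE handles correlation within centres. Neither restores comparability in the subset.

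At stake is the mortality part of the hypothesis, because items (3) and (4) are the only Aim 1 items that address death or morbidity. Items (1) and (2) are not affected. If the gum has no effect on birth weight, this route produces no distortion.

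**Working it through.** **The plan's own figure.** 8 sites × 1170 = 9360. After 30% loss, 9360 × 0.70 = 6552, or 3276 per arm. The total is consistent with the per-site number. It cannot be related to items (3) and (4), because no under-2000 g share or mortality is given, and the 33% in Section G1 is not stated for under-2000 g births.

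**A result that needs no rates.** Suppose the gum removes the same proportion of births at every weight below 2000 g and leaves weight-specific mortality alone. Deaths and infants in the subset are then multiplied by the same factor, so their ratio does not move. Conditional survival is exactly null, however many small births were prevented.

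**Illustration (all rates assumed).**
- Under-2000 g share: 5% of births, in equal lighter and heavier halves.
- Mortality: 60% in the lighter half, 20% in the heavier half, 1% at 2000 g or more.
- Infants shifted to 2000 g or more take on the 1%.

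Per 1000 control births, 50 are under 2000 g. Subset deaths are 25 × 0.6 + 25 × 0.2 = 20.0, a risk of 40.0%. Total deaths are 20.0 + 950 × 0.01 = 29.5.

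With 33% fewer, 16.5 infants shift and 33.5 remain.
- Subset deaths D = 0.6 × (lighter remaining) + 0.2 × (heavier remaining).
- Conditional RR = (D / 33.5) / 0.400.
- Total deaths = D + 966.5 × 0.01 = D + 9.665.
- All-births RR = total / 29.5.

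| Who shifts | Lighter / heavier remaining | D | Conditional RR | Total deaths | All-births RR |
|---|---|---|---|---|---|
| Heavier half only | 25 / 8.5 | 16.70 | 1.25 | 26.4 | 0.89 |
| 60/40 toward heavier | 18.4 / 15.1 | 14.06 | 1.05 | 23.7 | 0.80 |
| Uniform | 16.75 / 16.75 | 13.40 | 1.00 | 23.1 | 0.78 |
| 60/40 toward lighter | 15.1 / 18.4 | 12.74 | 0.95 | 22.4 | 0.76 |
| Lighter half only | 8.5 / 25 | 10.10 | 0.75 | 19.8 | 0.67 |

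**Varying the fixed assumptions** (33% fewer, shifts within 60/40, share 2–8%, mortality at 2000 g or more 0.5–2%). The conditional RR depends on neither of the last two and stays at 0.95–1.05. The all-births RR has these extremes:
- Share 8%, mortality 0.5%, 60/40 toward lighter: (20.384 + 946.4 × 0.005) / (32 + 920 × 0.005) = 25.116 / 36.6 = 0.69.
- Share 2%, mortality 2%, 60/40 toward heavier: (5.624 + 986.6 × 0.02) / (8 + 980 × 0.02) = 25.356 / 27.6 = 0.92.

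**A smaller effect.** With 10% fewer (5% share, 1% mortality; 45 remain, 5 shift), D is 18.2, 18.0 and 17.8 for 60/40 toward heavier, uniform and 60/40 toward lighter. Conditional RRs are 1.01, 1.00 and 0.99. Totals, adding 955 × 0.01 = 9.55, are 27.75, 27.55 and 27.35, giving all-births RRs of 0.94, 0.93 and 0.93.

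**No death prevented.** If shifted infants keep their original mortality, total deaths stay at 29.5 (RR 1.00), yet the conditional RRs in the table are unchanged. In that case the joint outcome, born under 2000 g and dead, per birth, has RR 16.7/20 = 0.835, 13.4/20 = 0.67 or 10.1/20 = 0.505 for heavier-only, uniform and lighter-only shifts.

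**The case against.** **The gap can be partly closed from the existing list.** Under-2000 g deaths per birth equal item (2) × (1 − item (3)), so a careful reader could see flat survival beside a fall in small births. This stands as partial mitigation. The calculation is not planned, however, and deaths at 2000 g or more would still be missed.

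**A reader might infer that Section G1 sets up a second, rival neonatal outcome that could be chosen after the data are seen.** The text does not support that. The phrase follows directly on preterm birth and reads more naturally as shorthand for items (3) and (4), or as outcomes linked to preterm birth, which would be another group formed after allocation. It is unclear and does not cure Aim 1, but it is not a demonstrated contradiction.

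**A reader might also infer that a fall in deaths of about 20% would be hidden, or that benefit would appear as harm.** Neither is established. The fall runs from 8% to 31% when the assumptions vary, is 6–7% for a 10% shift, and is zero if shifted infants keep their mortality. The 1.25 needs every shifted infant to come from the heavier half. At 1.05, with about 66/164 against 46/110 deaths, the 95% interval is roughly 0.79 to 1.40 before clustering, so looking worse could not be told from noise.

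**The joint outcome has its own flaw.** It can fall when no death is prevented, so it cannot serve as evidence on mortality.

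**Conclusion.** The concern holds. As written, items (3) and (4) compare subsets that the intervention may itself reshape, and nothing in Section G2 handles this. Conditional survival may look unchanged, worse or better in a way that does not track deaths per birth, and the direction cannot be predicted.

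The structural point rests on the text alone. The size does not: every birth-weight share and mortality used here is an assumption, so the calculated ranges show what is possible and do not estimate what will happen. The condition for any distortion is that the gum changes which infants are born under 2000 g, which is what the trial hopes for.

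**What to change.** Before outcomes are compared by arm, restate items (3) and (4) in Section D with births as the denominator, and align the wording in Section G1.

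- **Where 30-day status is already obtained for all infants:** use death by day 30 per birth, and death or composite morbidity by day 30 per birth. Including death in the second keeps deaths from removing infants from the morbidity outcome.
- **Otherwise:** report *born under 2000 g and dead by day 30* and *born under 2000 g and dead or with composite morbidity by day 30*, per birth and always beside outcome (2). Do not interpret them as neonatal mortality or morbidity.
- **Counting:** state how stillbirths and multiple births count.
- **Flow by arm:** report enrolled women, pregnancies, births and births with known 30-day status. The births denominator also arises after allocation, given preconception and postpartum enrolment and the statement that "we have accounted for a 30% loss to follow up". These counts make any imbalance visible but do not remove it.
- **Within-subset rates:** keep them as clearly labelled conditional, descriptive results beside outcome (2), not as evidence of a treatment effect on survival.

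**Cost.** The joint version is a change of wording and needs no infants beyond those Aim 1 already follows. Because the listed visits end at delivery, how 30-day status is obtained needs stating even for Aim 1 as it stands. The event rate falls. In the example, assuming one birth per retained woman, 3276 × 0.05 ≈ 164 infants and 164 × 0.40 ≈ 66 control deaths, which is 40% of the subset but 2.0% of 3276 births. Any precision statement for these outcomes must be restated. Deaths at 2000 g or more are missed unless their 30-day status is already available, and obtaining it would be added follow-up.
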